11.2 TEMPORARY OR PERMANENT TREATMENT/STUDY DISCONTINUATION

Patients should continue using the product whenever possible and permanent discontinuation should be only a last resort. Any treatment discontinuation should be fully documented on the eCRF.

11.2.1 Temporary treatment discontinuation

Temporary treatment discontinuation may be considered by the Investigator because of a suspected AE. Treatment can be resumed under close clinical monitoring once the Investigator has considered an association of the treatment with the occurrence of the event unlikely and if the selection criteria for the study are still met (refer to [Section 8](#)).

The duration of all temporary treatment discontinuations should be recorded by the Investigator in the eCRF.

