2 ASSESSMENT CHART

2.1 STUDY DESIGN

2.1 ASSESSMENT CHART

Study period	Run-in*		Period I (double-blinded)		Period II (follow-up)	
	V1	V2	V3	V4	V5	V6
Visit	V1	V2	V3	V4	V5	V6
Time (weeks)	-2	0	2	4	8	16
Informed consent	X					
Inclusion/Exclusion criteria	X					
Demography/Medical history	X					
Physical examination	X	X		X	X	X
Randomization		X				
TSS, TNSS, TOSS, TTSS		X	X	X		
VAS		X	X	X		
PRQLQ		X		X	X	X
Incidence, intensity, and duration of exacerbations					X	X
Use of rescue medication			X	X	X	X
Provide/return diary		X	X	X	X	X
Dispensation of double blind treatment		X				
Dispensation of Lertal				X		
Concomitant treatment		X	X	X	X	X
Adverse Event monitoring		X	X	X	X	X
Product accountability			X	X	X	X

* Visit 1 and Visit 2 may take place on the same day.

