8.1 INCLUSION CRITERIA

Each patient must meet all of the following inclusion criteria:

- Age 6 to 12 years
- Male or female
- Diagnosis of allergic rhinoconjunctivitis

- Hypersensitivity to dust mites or pollen confirmed with skin-prick test (wheal and redness, ≥ 3 mm more extended than control) performed in the previous 12 months
- Total Symptoms Score (TSS) ≥ 15 and at least 1 for nasal congestion
- Written informed consent of patient and of parent or legal guardian

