9 STUDY TREATMENTS

9.1 INVESTIGATIONAL PRODUCT

Lertal® double-layer tablets

Lertal[®] is a novel food supplement. Each tablet contains the following active ingredients in a double-layer “fast-slow” release tablets:

- Quercetin 150 mg: a natural flavonoid that inhibits the release of histamine, leukotrienes, PGD2, IL (IL-6, IL-8, TNF-alpha).
- *Perilla frutescens* 80 mg: A dry extract of the seeds containing rosmarinic acid, luteolin, apigenin and crysoeriol that inhibits the release of histamine and expression of interleukins (IL-6, TNF-alpha).
- Vitamin D3 5 mcg (200 IU), which contributes to the normal function of the immune system.

One oral Lertal[®] tablet a day is to be administered together with standard therapy (antihistamine) for 4 weeks by patients randomized to the active treatment group + standard therapy during Period I. During Period II, patients taking Lertal[®] tablets in Period I continue taking one tablet a day for an additional 4 weeks if allergic to pollen or 12 weeks if allergic to dust mites. Lertal[®] is not associated with standard therapy during Period II.

A patient that concludes treatment Period I and still presents symptoms that do not permit suspension of standard therapy is considered a non-responder and will not take part in Period II of the study. The patient will be discontinued from the study and will be treated as deemed appropriate by the Investigator.

Lertal[®] will be provided by the Sponsor free of charge.

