9.4 METHOD OF ASSIGNING PATIENTS TO TREATMENT GROUP

For Period I, patients will be randomized with a 1:1 ratio to one of the two treatments (oral Lertal[®] tablets +standard therapy or placebo tablets + standard therapy).

The study product and placebo will be provided in identical boxes and will be identified with a four-digit box number.

The randomization list will be stratified by type of allergy and generated according to permuted blocks codes by an independent statistician through a validated SAS program[®] Software Version 9.4.

The randomization process will be centralized and the assignment to one of the treatments will be carried out through the web-based Electronic Case Report Form (eCRF) system by designated site personnel. When a patient is considered eligible (i.e. he/she fulfils all the inclusion criteria and does not present any exclusion criteria of the Study Protocol), site personnel will access the system in a dedicated section, using a personal account to receive the box number for the incoming patient and will confirm the assignment into the system. Each box number is linked to a treatment code through the randomization list.

A randomized patient is defined as a patient who is registered and is assigned to a box number by the eCRF.

To ensure an adequate number of patients with both types of allergies (pollen and dust mites), the enrollment of patients with dust mite allergies will be blocked should these patients represent 60% of the study population before spring 2018.

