9.10 RESCUE AND CONCOMITANT MEDICATION

Rescue therapy may be used as needed, and is defined as an increment of standard therapy (increase in dose, frequency of administration or change of antihistamine) in Period I, and as the use of any antihistamine in Period II. The use of rescue treatment will be recorded on the CRF and will be evaluated as efficacy variable.

The following medications are prohibited during the study:

- Systemic or intranasal corticosteroids
- Leukotriene antagonists
- Sodium cromoglycate

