13.2.2 Statistical Analysis

All data collected in the study will be listed and summarized as appropriate as described below. Continuous data will be summarized by means of common descriptive statistics: mean, standard deviation (SD), median, first and third quartiles, minimum and maximum. Categorical data will be presented by absolute and relative frequencies (n and %) or contingency tables.

For the safety analysis, patients will be included in based on available assessments; no missing data handling approach will be applied. For efficacy analyses, patients who interrupt treatment will be considered as “failures” for qualitative variables and their missing quantitative data will be substituted according to the LOCF method (Last Observation Carried Forward). Unless stated otherwise, two-sided p-values <0.05 will be considered statistically significant.

All statistical tables, listings, figures and analyses will be generated using SAS® release 9.4 or later (SAS Institute Inc., Cary NC, USA).

No interim analyses are planned.

Further details about data analysis will be provided in the Statistical Analysis Plan document.

All data about patient demographics and baseline characteristics will be summarized on the ITT population by treatment group by means of summary descriptive statistics.

The number and percentages of subjects meeting all eligibility criteria at screening will be provided. The analysis populations will be described and the reasons for excluding a patient from any particular population will be provided with the number of protocol deviators per each criterion.

A complete description of patients’ disposition will be provided specifying the number of randomized patients, the number of patients at each visit, the number of completed and discontinued patients and the reason for the discontinuation.

Medical history data will be presented by Medical Dictionary for Regulatory Activities MedDRA dictionary system organ class (SOC) and preferred term (PT).

Concomitant medications and significant non-drug therapies will be presented by WHO Drug Dictionary ATC class and preferred term.

- **Primary endpoint**

Changes from baseline of TSS scores will be calculated after 4 weeks of treatment. The between-group analysis will be performed by means of a t-test for independent samples or analogous non-parametric test.

- **Secondary endpoints**

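### The restart rule in Section 11.2.1 re-applies entry criteria that improvement, or in Period I the required antihistamine, can make a child fail

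*Combined protocol and SAP*

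**What the plan says.** Section 11.2.1 allows a pause for a suspected adverse event. Treatment may resume, under close monitoring, when two conditions hold together: the investigator has judged a link to the treatment unlikely, and "if the selection criteria for the study are still met". The second condition refers to Section 8 as a whole and names no exception.

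Three parts of Section 8 matter here:

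- Section 8.1 requires "Total Symptoms Score (TSS) ≥ 15 and at least 1 for nasal congestion".
- Section 8.2 excludes children who use antihistamines continuously.
- Section 8.2 also excludes children with an inadequate washout, set at 5-10 days for cetirizine, fexofenadine, loratadine, desloratadine and hydroxyzine.

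Section 9.3 then gives every child in both arms an investigator-chosen antihistamine for the 4 weeks of Period I. In Period II this co-therapy ends: Section 9.1 says that the product "is not associated with standard therapy during Period II".

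Section 11.2 sets the general aim: keep children on the product where possible and stop permanently only when nothing else will do.

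**The concern.** A restart rule after an adverse event should ask whether it is safe and sensible to go on. This one asks whether the child would still qualify to enter the trial. Two of the entry requirements are ones that the trial itself is expected to change.

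- **Symptoms.** Lowering the TSS is the purpose of treatment. A child who has improved may no longer qualify, while a child who has not improved still does. Restart then depends on the primary variable. The wording is the same in both arms, but if the product works, more of its paused children would fall under the threshold.
- **Antihistamine.** A child who follows Section 9.3 is taking the class of drug that Section 8.2 rules out.

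A site that follows the text would permanently stop children whose event was judged unlikely to be related. A site that follows the apparent intent would restart them, in breach of the text. With about 17 sites and no guidance on which criteria to re-check, practice may differ from site to site.

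**Working it through.** The plan states no figure on this point, so the check sets the sections side by side, with a little arithmetic on the score.

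**1. Symptom criterion**

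Inputs: nine symptoms, each scored 0 to 3 (Section 10.1.1); overall TSS is the mean of a 12-hour and a two-week score (Section 10.1.1); entry needs TSS of at least 15 and congestion of at least 1 (Section 8.1); a responder has at least a 30% fall in TSS (Section 6.2). I assume that the entry threshold refers to the overall score.

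- Maximum TSS = 9 × 3 = 27. As the mean of two whole numbers, the score moves in steps of 0.5.
- A child who enters at 15 fails the criterion after any fall, since the next value down is 14.5.
- A responder with baseline B has TSS of at most 0.7 × B. For B = 21 this is 0.7 × 21 = 14.7, so the highest possible value is 14.5. For B = 21.5 it is 15.05, so a value of 15 is possible. Every child with a baseline from 15 to 21 who is a responder at the time of the check therefore fails the restart criterion.
- At the maximum baseline of 27, a child must fall by more than 27 − 15 = 12 points, or 12/27 = 44%, to fail it.
- Congestion acts separately. A child whose congestion goes to 0 fails even with TSS still at 15 or more.

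The assessment chart in Section 2 schedules TSS at Visits 2, 3 and 4 only. A pause between visits, or in Period II (Visits 5 and 6), has no scheduled score with which to apply the test.

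**2. Antihistamine criteria (Period I)**

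| Section 8.2 exclusion | What Section 9.3 requires | Literal result at restart |
|---|---|---|
| Continuous antihistamine use | An antihistamine for 4 weeks | Exclusion present while the child continues it |
| No 5-10 day washout of five named drugs | Drug chosen by the investigator | Exclusion present if the drug is one of the five and is continued |

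The first row assumes that 4 weeks of standard therapy counts as continuous use. No dosing schedule is given, but this is the natural reading. In Period II standard therapy has ended, so this conflict with required therapy is confined to Period I. The symptom conflict is not.

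**3. Evidence of intent**

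- The chart row "Inclusion/Exclusion criteria" is marked at Visit 1 only.
- Section 9.4 applies the criteria at box assignment: "When a patient is considered eligible (i.e. he/she fulfils all the inclusion criteria".
- Section 9.10 has its own on-study list, introduced by "The following medications are prohibited during the study". It has three entries (systemic or intranasal corticosteroids, leukotriene antagonists, sodium cromoglycate), and none is an antihistamine.
- Section 9.10 also permits more antihistamine as rescue, which "is defined as an increment of standard therapy (increase in dose, frequency of administration or change of antihistamine) in Period I".

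All four point to entry-only use. None of them amends the condition in Section 11.2.1, which is the one place that carries Section 8 forward into treatment.

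**The case against.** The strongest reply is that these are plainly entry criteria. A washout is by nature a test made before enrolment, and the chart and Sections 9.4 and 9.10 fit that view. Read otherwise, Section 8.2 would make every treated child ineligible within days. This stands as evidence of what the authors probably meant, and many sites may act on it. It does not settle the text. If the clause meant only that the criteria were met at entry, it would do nothing, since every randomised child was to have met them. So some criteria are presumably to be re-checked, and the plan does not say which.

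Two stronger readings are tempting, and the documents do not support them.

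- **A reader might infer that no child who complies with the protocol could ever restart in Period I.** That goes too far. Section 11.2 speaks of the product, but Section 11.2.1 speaks of treatment, and Sections 9.4 and 11.1 describe each treatment as tablet plus standard therapy. If the antihistamine is paused too, use is no longer continuous, and the washout is satisfied after 5-10 days. The washout line also names only five drugs. The bar applies to a child who continues the antihistamine during the pause.
- **A reader might infer that the restart rule causes children to be coded as failures.** Section 13.2.2 says "For efficacy analyses, patients who interrupt treatment will be considered as" failures for qualitative variables. Read as literally as Section 11.2.1, that already covers a child who pauses, whether or not restart follows. The coding cannot be attributed to the restart rule.

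It is also fair to say that Section 9.10 does not contradict the restart rule, because it governs concomitant drugs and is silent on restart. The principle in Section 11.2 is qualified by what is possible, so the tension with it arises only when the restart rule is applied literally.

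**Conclusion.** The point holds and is minor. Section 11.2.1 states a rule which, followed as written, bars from restart a child whose TSS has fallen below 15 or whose congestion has resolved and, in Period I, a child who continues the required antihistamine. That is a wrongly specified rule rather than a missing detail, because a site that obeys it turns pauses into permanent stops after events judged unlikely to be related.

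The size is unknown. The documents give no rate of temporary stops and no distribution of baseline TSS, so I claim no effect on power or on the treatment estimate. The effect on the primary analysis is probably small: Section 11.2.3 keeps stopped children in follow-up, and last observation carried forward replaces only values that are missing. What can be said with confidence concerns the text; how sites would apply it is not known.

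**What to change.** Amend Section 11.2.1 to say that the TSS and nasal congestion criterion, and the antihistamine use and washout criteria, apply at entry only. Then state that restart requires all of the following:

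1. the adverse event is judged unlikely to be related to the treatment;
2. none of a fixed list of exclusions is present: uncontrolled asthma, acute or chronic sinusitis, hypersensitivity to the product or its excipients;
3. no drug prohibited in Section 9.10 is in use.

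The list should be closed rather than given as examples, or sites are again left to choose. The amendment should also say whether a pause covers the tablet alone or the antihistamine as well.

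The cost is a short protocol amendment and a memo to sites, with no added patients, visits or assessments. The drawback is that some children with a shortened course stay on treatment.

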11.2.2 Permanent treatment discontinuation

The patients may withdraw from treatment at any time and irrespective of the reason, or this may be the Investigator's decision. A patient that concludes treatment Period I and still presents symptoms that do not permit interruption of standard therapy is considered a *non-responder* and will be discontinued from the study. All efforts should be made to document the reasons for treatment discontinuation on the eCRF. Discontinued patients will not be replaced.

11.2.3 Handling of patients after permanent treatment discontinuation

Patients will be followed-up according to the study procedures as specified in this protocol up to the scheduled date of study completion, or up to recovery or stabilization of any AE, whichever comes last.

If possible, and after the permanent discontinuation of treatment, the patients will be assessed using the procedures normally planned for the last visit.

All cases of permanent treatment discontinuation should be recorded by the Investigator in the CRF when considered as confirmed.

For patients who fail to return to the site, the Investigator should make the best effort to re-contact the patient's parents and to determine their child's health status. Attempts to contact such patients must be documented in the patient's records.

12 DATA MANAGEMENT

12.1 DATA COLLECTION

Designated Investigator staff will enter the data required by the protocol onto the Electronic Case Report Forms using fully validated software that conforms to 21 CFR Part 11 requirements. Designated Investigator site staff will not be given access to the EDC system until they have been trained.

Web based software will be used: no installation procedure will be needed. Investigator site qualified personnel will be allowed to access to the eCRF by means of a 'login mask' requiring Username and Password, and it will be possible to read, modify and update only the information reported at his/her site. Each page should report site code and patient code.

The Investigator must certify that the data entered onto the Electronic Case Report Forms are complete and accurate.

12.2 DATA MANAGEMENT AND QUALITY CONTROL

The Data Manager of the Contract Research Organization (CRO) working on behalf of the Sponsor will review the data entered onto the eCRFs by investigational staff for completeness and accuracy, and will instruct the site personnel to make any required corrections or additions. He/she will perform the cleaning session reviewing the warning messages raised by on-line checks and by running post-entry checks by means of validation programmes and data listings specific for the study. During this process, if clarification is needed, the Data Manager will raise queries by means of data query forms through the WEB application. Designated Investigator site staff is required to respond to the query and the Data Manager will make the correction to the database on the basis of the query response.

The Data collection and the Queries flow as well as the on-line and off-line control checks will be detailed in the Data Management Plan and Data Validation documents.

Concomitant medications entered into the database will be coded using the WHO Drug Reference List, which employs the Anatomical Therapeutic Chemical classification system. Medical history/current medical conditions and adverse events will be coded using the Medical dictionary for regulatory activities (MedDRA) terminology.

The occurrence of any protocol deviations will be determined. After these actions have been completed and the database has been declared to be completed and accurate, it will be locked and made available for data analysis. Any changes to the database after that time can only be made upon documented agreement within the Study Team.

13 STATISTICAL CONSIDERATIONS

[figure not shown]
13.1 DETERMINATION OF SAMPLE SIZE

160 patients are to be enrolled in this study.

Confidential

A sample of 72 patients for each group will have an 80% power to detect an effect size on the primary variable ($\delta = |\mu_1 - \mu_2| / \sigma$) of 0.47 (medium effect size) (12), using an independent samples t-test with a two-tailed significance level of 5%.

A sample size of 80 patients per group will account for an expected dropout rate of 12% (13), using Freedman's formula (*Control Clin Trials*, 1990): $n' = 100 * n / 100 - x$, where x is the expected dropout rate.

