13.2 STATISTICAL METHODS

13.2.1 Analysis populations

Patients without a valid or adequately obtained Informed Consent Form (ICF) will be excluded from any analysis population.

The following analysis populations have been defined for these statistical analyses:

- Safety: All randomized patients who took at least one dose of study product.
- Intention to treat (ITT): All randomized patients who took at least one dose of study product and have at least baseline and one post-baseline assessment of the primary efficacy variable. Patients who interrupt treatment will be considered as “failures” for qualitative variables and their missing quantitative data will be substituted according to the LOCF method (Last Observation Carried Forward).
- Per protocol (PP): All randomized patients who completed Period I and did not have significant protocol violations that regard inclusion/exclusion criteria or can condition the efficacy evaluation.

The efficacy analysis will be performed on the ITT population and also on the PP population as a supportive analysis for the primary endpoint and reported overall and by planned treatment group. Safety will be evaluated in the Safety population and reported overall and by actual treatment group.

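### The plan's own dropout formula gives 82 patients per group at 12% dropout, not the stated 80; 80 per group covers exactly 10%

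*Combined protocol and SAP*

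**What the plan says.** All the inputs are in section 13.1 (Determination of sample size).

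- Enrolment target: "160 patients are to be enrolled in this study".
- Evaluable number: "A sample of 72 patients for each group will have an 80% power to detect an effect size on the primary variable". The effect size is 0.47, labelled medium, and the calculation is made "using an independent samples t-test with a two-tailed significance level of 5" per cent.
- Dropout step: "A sample size of 80 patients per group will account for an expected dropout rate of 12" per cent. The rate is supported by reference 13, and a published formula is named, n' = 100n/(100 − x), "where x is the expected dropout rate".

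Two other sections affect how many patients reach the primary analysis. Under section 13.2.1 the ITT set consists of treated patients who "have at least baseline and one post-baseline assessment of the primary efficacy variable", with missing values carried forward. Section 11.2.3 adds that after permanent discontinuation, where possible, "the patients will be assessed using the procedures normally planned for the last visit". Section 11.2.2 rules out replacing discontinued patients.

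**The concern.** The plan names its formula and gives both inputs, so the result is determinate, and 80 is not that result. Either the dropout rate or the group size is wrong as written. The sentence assures the reader that 12% dropout has been allowed for. Under the plan's own rule 80 per group falls slightly short of that, and with no replacement nothing later in the plan makes up the difference. The sample-size justification is also likely to be repeated in the study report, where any reader can redo the sum.

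**Working it through.** **Inputs (section 13.1):** n = 72 per group; effect size 0.47; two-sided 5% independent-samples t-test; 80% power; dropout x = 12; stated result 80 per group, 160 in total. Allocation is 1:1 (section 9.4).

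**1. The plan's starting figure.** The noncentral t distribution gives power 0.7998 at 72 per group for an effect of 0.47. The exact solution for 80% power is n = 72.04. The 72 is sound, so the problem is confined to the dropout step.

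**2. The dropout step as the plan defines it.**

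n' = 100 × 72 / (100 − 12) = 7200/88 = 81.8, rounded up to 82 per group, 164 in total.

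The shortfall is 82 − 80 = 2 per group, 4 in total.

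**3. Other readings that might give 80.**

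| Reading | Calculation | Result |
|---|---|---|
| Simple multiplication | 72 × 1.12 = 80.64 | 81 |
| Formula without brackets, as it appears in the text | 100 × 72/100 − 12 | 60 |
| 11.5% rounded to 12% | 72/0.885 = 81.4 | 82 |
| Starting from 71 | 71/0.88 = 80.7 | 81 |
| 10% dropout | 72/0.90 | 80 exactly |

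Only 10% gives 80.

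**4. Power if every dropout is lost.** 80 × 0.88 = 70.4 per group remain, and 80 × 0.12 = 9.6 are lost.

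| Analysed per group | Power at 0.47 | Effect detectable with 80% power |
|---|---|---|
| 70 | 0.788 | 0.477 |
| 70.4 | 0.791 | 0.476 |
| 72 | 0.800 | 0.470 |
| 80 | 0.840 | – |

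**5. Power if some dropouts stay in the ITT set.** Getting back to 72 needs 72 − 70.4 = 1.6 of the 9.6 dropouts per group, or 1.6/9.6 = 17%. If retained dropouts show the full effect, power is 0.800 with 17% retained, 0.817 with 50% and 0.840 with all.

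The plan says nothing about the effect to expect in carried-forward patients, so the following is an assumption shown over a range. Let them show a fraction f of the full effect, with the SD unchanged. With all 9.6 retained, the average effect is 0.47 × (70.4 + 9.6f)/80:

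- f = 1: 0.470, power 0.840
- f = 0.5: 0.47 × 75.2/80 = 0.442, power 0.793
- f = 0: 0.47 × 70.4/80 = 0.414, power 0.739

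At f = 0.5, retention neither gains nor loses much (0.791 to 0.793 whatever share is kept). Below that, carrying patients forward costs power. This last effect belongs to the missing-data method, not to the arithmetic slip.

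**The case against.** The strongest reply is that the slip changes nothing of substance. The gap is 2 in 82, or 2.4%, and at worst step 4 costs about one point of power. That scenario is also an upper bound on the number lost. Section 13.1 does not say that the 12% is loss by week 4, when the primary endpoint is measured, whereas participation lasts about 10 to 18 weeks (section 7.2.1). If the 12% covers the whole study, fewer than 9.6 per group would be missing at week 4. Patients who leave after the week 2 visit remain in the ITT set.

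Most of this stands, and it limits the point to a minor one. It does not repair the sentence, which relies on the formula and not on ITT retention. Two qualifications apply. The last-visit assessment in section 11.2.3 is weak support for retention, because the assessment chart in section 2 collects TSS only at Visits 2, 3 and 4; if the last visit means Visit 5 or 6, no TSS is scheduled there. The supportive per-protocol analysis requires completion of Period I, so carrying observations forward does not help it.

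**Conclusion.** The concern holds. Under the plan's own formula, 12% dropout requires 82 per group (164 in total), and the stated 80 corresponds to exactly 10%. The severity is minor. If every dropout is lost by week 4, power is about 79% against the stated 80%, and the effect detectable with 80% power is about 0.48 against 0.47. That rests on the full 12% being missing from the primary analysis, which the plan does not state. If about one dropout in six has a post-baseline TSS and shows the full effect, nominal power is back at 80%. The trial is not shown to be materially underpowered.

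**What to change.** Restate one sentence in section 13.1, with no added patients, in one of two ways:

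1. Say that 80 per group allows for 10% dropout.
2. Keep the referenced 12% and say that, if all dropouts are lost from the analysis, about 70 completers per group give about 79% power for an effect size of 0.47, and that the ITT set with last observation carried forward may retain more.

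The second is preferable. The first departs from the referenced rate, and nothing in the document supports 10% except that it fits 80. The cost of the second is a slightly less favourable power figure. Raising the target to 82 per group would also make the sentence true, but four extra patients are not needed to correct a discrepancy of this size. In the same edit, write the formula with its brackets, 100n/(100 − x), if they are missing from the source document as well.
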